5. STUDY INTERVENTIONS

The Template for Intervention Description and Replication (TIDieR) checklist has been used to guide the description of the study interventions⁸⁰ to facilitate future results interpretation, as well as dissemination and replication. Table 4 illustrates the standard elements **common to both interventions**. Participating clinicians will be trained and certified in study protocols and intervention specific content (see below for additional details).

Table 4. Common Intervention Elements (Experimental & Comparison Groups)

Initial intervention period	12 weeks; # of visits determined collaboratively by provider and patient (once minimum is reached)
Restrictions	No outside care during main 12-week intervention period
Ongoing care	If recurrence or worsening of BRLP after 12 weeks, can receive care in assigned group
Procedures	Appointment reminders, follow up for missed appointments provided
Standardized information	Modified “Back in Action” book covering evidence based BRLP messages
Over the counter medication	As necessary
Location	UMN affiliated outpatient clinic in Minneapolis

The main intervention period is 12 weeks long. All patients will be asked to limit treatment to their assigned intervention for the main 12-week intervention period. Participants in both groups will be monitored during the intervention phase for the development of exclusion criteria impacting participant safety which will result in withdrawal from the study intervention along with a referral for appropriate care (e.g. development of progressive neurological deficits). All patients will receive basic standardized information regarding the etiology, prognosis, and basic self-management of back-related leg pain.

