5.3.3. Prohibited Interventions

Participants will be asked to limit treatment to their assigned intervention for the length of the initial 12-week intervention period. However, participants retain the right to discontinue study treatment at any time. Providers will be taught to refrain from delivering interventions that fall outside the scope of the study protocols (see above).

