5.5. Intervention Fidelity

We will apply robust fidelity activities based on our experience from previous studies to facilitate future intervention replication, internal validity, and accurate interpretation of outcomes.⁹⁶⁻⁹⁸ This includes training and certification (described in section 5.1); use of standardized intervention checklists to guide clinicians through each session; and monthly group meetings with key investigators to receive ongoing coaching in intervention protocols.⁹⁹

Fidelity assessments. All intervention visits will be video recorded with patient consent; a random selection of 10% will be reviewed for fidelity by study investigators. Standardized fidelity instruments will be used to document required, allowed, and prohibited intervention activities and elements. Individualized feedback will be provided to providers as needed based on fidelity assessments.^{99,100} Additionally, standardized treatment clinical report forms will be reviewed for required, allowed, and prohibited interventions.

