6.2.2 Enrollment, Baseline, and/or Randomization

Enrollment

Enrollment is defined as the date of randomization at which point all eligibility criteria are confirmed and the individual has agreed to participate; this is recorded on a case-report form. AEs will be collected after the participant is enrolled. Participants will be told to contact study staff and/or providers about any health-related changes they experience. 40-50 participants will be enrolled.

Baseline Assessments

Baseline measures will include demographic, occupational, clinical and behavioral characteristics, and mediating outcomes including the NIH Research Task Force's minimum dataset for chronic LBP.¹¹¹ The following will be collected at baseline:

- Demographics including PhenX ToolKit's core measures for Social Determinants of Health¹⁵⁵
- Quebec Task Force Classification for spinal disorders⁹⁵ and Pain Detect Questionnaire to identify neuropathic presentations of BRLP¹⁵⁶
- STarT Back Screening tool¹¹²

Clinical Outcome Measures

- BRLP and LBP frequency over the past week (number of days with BRLP symptoms).
- BRLP and LBP intensity (0-10 pain scale) over the past week using the ordinal 11-box NRS (0=no BRLP/LBP, 10=the worst BRLP/LBP possible).
- Disability will be measured with the 23-item Roland Morris Disability Questionnaire which was adapted and validated for BRLP.¹¹⁵
- PROMIS-29 +2 includes measures of pain interference with normal activities, physical function, fatigue, sleep disturbance, anxiety, depression, and participation in social roles and activities.¹¹⁶⁻¹¹⁸ The PROMIS-29+2 also provides a preference-based summary of health-related quality of life.¹¹⁹ Other PROMIS/NIH Toolbox instruments will include social emotional support;^{116,117} domain-specific life satisfaction (e.g. work, family, housing);¹²⁰ and perceived stress.¹²²
- Productivity loss related to BRLP (e.g., missed work, reduced productivity while at work) will be assessed using questions from the Institute for Medical Technology Assessment's productivity cost questionnaire.¹²³

Behavioral Outcomes

The following behavioral outcomes are chosen because they're most likely to affect the experimental intervention:

- Chronic pain coping behaviors will be measured using the Chronic Pain Coping Inventory - 2-item version.¹²⁸
- Over-the-counter and prescription medication use²⁰ for BRLP, including class of medication and frequency of use.

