- Healthcare use for BRLP including MRIs, injections, hospitalizations, surgeries, and provider-based visits.²⁰
- Physical activity levels (e.g. amount of sedentary activity) measured with the International Physical Activity Questionnaire.¹²⁹

Mediating Outcomes

Mediating outcomes and targets of the intervention theorized to affect the clinical and behavioral outcomes will also be collected to inform protocol refinement. These include:

- BRLP related capabilities (e.g. knowledge, skills, physical capacity), opportunities (e.g. available resources), motivations (e.g. optimism)⁵¹⁻⁵³ for participants enrolled into supported self-management.
- Beliefs related to self-efficacy as measured by confidence in ability to manage daily activities, symptoms, emotions, and social interactions (PROMIS self-efficacy for managing chronic conditions);¹³⁰ the chronic pain acceptance questionnaire will also be administered.¹⁵⁷
- Fear-avoidance beliefs using the Fear-avoidance Beliefs Questionnaire¹³¹
- Catastrophizing measured using the 13-item Pain Catastrophizing Scale;¹³² it uses a 5-item point scale (0=not at all, 4 all the time) and has internal consistency and validity.
- Expectations about back pain treatments (HEAL items).¹³⁵

Qualitative measures

Qualitative measures will be collected from enrolled subjects, as well as providers regarding their views of barriers, facilitators, affordability, practicality, effectiveness, acceptability, and equity.

As part of the supplemental aims, qualitative information will be collected from other stakeholders with pain who are underrepresented in CIH LBP/BRLP research to explore their views of barriers and facilitators to care for LBP/BRLP.

Randomization

In the pilot study, randomization precedes intervention administration. Randomization will occur within 21 days of completing the first baseline screening visit. Participants who are not randomized within this time frame will repeat the in-person screening. Interventions will be initiated within 14 days of randomization/enrollment.

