6.2.4 Follow-up Visits

Intervention Visits (M0-M6)

The following information will be collected at each intervention visit in the pilot study, which will occur as needed throughout the six months, as there is no set schedule of treatments:

- Treatment administered – study providers will record treatment administered at each visit including required, allowed, and prohibited treatments.
- Adverse events (AEs)- participants will be asked about the occurrence of AE/SAEs by their treatment provider at each visit. The AE protocol described in section 7, Safety and Assessments will be initiated and adhered to for all AEs identified.

Weekly Follow-Up (\pm 3 DAYS)

Weekly outcomes will be collected electronically via direct patient self-report for six months; participants who are unable to provide electronic data will be contacted directly by blinded study staff who will ascertain outcomes. Additional information related to data collection and quality assurance is described in section 10.

Clinical Outcome Measures

- BRLP and LBP frequency and intensity

Monthly Follow-up (\pm 14 DAYS)

Monthly follow-up data (Months 1-6) will be collected electronically via direct patient self-report. Participants who are unable to provide electronic data will be contacted directly by blinded study staff who will ascertain outcomes, or they will be mailed a paper copy of the questionnaire to complete and return to the study team. Additional information related to data collection and quality assurance is described in section 10.

The following outcomes will be collected on a monthly basis for 6 months (\pm 14 days):

Clinical Outcome Measures

- Disability, PROMIS-29+2 measures, and productivity loss
- Adverse Events - participants will be asked if they experienced any potential adverse events associated with study interventions (e.g. increased pain, neurological symptoms, nausea)

Behavioral Outcome Measures

- BRLP-related medication and healthcare use

Month 2 Follow-up (\mp 14 DAYS)

Mediating Outcome Measures

- Satisfaction related to the patient-provider connection and healthcare environment (HEAL items).¹³⁵ Treatment expectations for the assigned intervention will also be assessed.

Month 3 Follow-up (\mp 14 DAYS)

Clinical Outcome Measures

- PROMIS/NIH Toolbox measures for social emotional support, domain-specific life satisfaction, and perceived stress.
- Global improvement will be measured using a 9-point scale ranging from completely recovered to vastly worse.¹⁵⁴

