9.4. Outcomes

9.4.1. Primary Outcomes

Primary outcomes for the pilot study are feasibility measures for the larger randomized trial including:

- Recruitment feasibility - Number of participants screened per month; percentage of screened participants who are female; percentage of screened participants who are minorities; participant views and perspectives on research participation
- Enrollment feasibility - Number of participants enrolled per month; percentage of enrolled participants who are female; percentage of enrolled participants who are minorities; participant views and perspectives on research participation
- Intervention acceptability and credibility feasibility - Percentage of enrollees not receiving any treatment; percentage of enrollees receiving prohibited treatments during the 12-week intervention phase (contamination); percentage of enrollees satisfied with treatment

- Participant treatment adherence feasibility - Percentage of enrollees attending required sessions; percentage of enrollees in the supported biopsychosocial self-management group reporting participation in home practice; percentage of enrollees in medical care group reporting taking medications as prescribed
- Provider fidelity feasibility - Percentage of provider visits where 100% of required intervention activities were delivered
- Data collection feasibility - Percentage of enrollees completing the month 3 assessment; percentage of enrollees completing the month 6 assessment; percentage of weekly pain severity and frequency assessments completed

Table 6. Feasibility Measures & Targets

Recruitment	≥40 screened/month (50% women, 25% minorities)
Enrollment	≥8 enrolled/month (50% women, 25% minorities)
Intervention acceptability, credibility	≤10% never receive any treatment; ≤10% receive prohibited treatments during 12-week intervention phase (contamination) ≥80% satisfied with treatment
Participant adherence	≥80% participants attend required sessions (SSM=4; MC=2) ≥70% of SSM participants report participation in home practices ≥70% of MC participants report taking medications as prescribed
Provider fidelity	Providers deliver 100% of required intervention activities on ≥70% of visits
Data collection	≥85% of participants complete 12 weeks follow up ≥80% of participants complete 25-week follow up ≥80% of weekly pain severity and frequency surveys completed

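### Does the 10% contamination target need a named data source before it can be judged?

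*Combined protocol and SAP*

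**What the plan says.** The target in Table 6 (9.4.1) is "≤10% receive prohibited treatments during 12-week intervention phase (contamination"). The outcome list in 9.4.1 expresses it as a percentage of enrollees, and 9.5 reports it by group among measures of participants' compliance. No data source or counting rule is given in either place.

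Two records could supply the count.

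- **Visit forms.** Under 6.2.4, "study providers will record treatment administered at each visit including required, allowed, and prohibited treatments". Section 5.5 adds that "standardized treatment clinical report forms will be reviewed for required, allowed, and prohibited interventions".
- **Monthly surveys.** Section 6.2.4 collects "BRLP-related medication and healthcare use" in months 1 to 6. The baseline text in 6.2.2 describes these domains as "Healthcare use for BRLP including MRIs, injections, hospitalizations, surgeries, and provider-based visits" and as over-the-counter and prescription drug use "for BRLP, including class of medication and frequency of use".

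The restriction itself also appears at two levels. Sections 5.2.1.3 and 5.2.2.3 list what study providers may not deliver or recommend. For participants, Table 4 (section 5) states "No outside care during main 12-week intervention period", and 5.3.3, headed Prohibited Interventions, states "Participants will be asked to limit treatment to their assigned intervention for the length of the initial 12-week intervention period".

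**The concern.** The measure is a primary outcome with a numeric limit, and section 14 has the phase II trial follow once the Table 6 targets establish feasibility. The field whose name matches the target is on the provider's visit form, which records what that provider administered. An injection or a visit obtained elsewhere would not normally appear there. An analyst who took only that field could report the target met however much outside care took place, while one who added the surveys could report it missed. At this sample size a few participants decide the result.

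There are secondary worries. SSM participants may receive rescue prescriptions under 5.3.2, so a survey report of a prescription drug must be sorted into permitted and outside use. A missing survey could be handled in more than one way. The second-line drug lists also differ in how they mention weak opioids.

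**Working it through.** **The limit in counts.** The plan gives no derivation of 10%, so there is no calculation to reproduce. With N = 40 to 50 (section 9.1), the largest passing count is floor(0.10 × N): 4 of 40 and 5 of 50. The next count fails: 5/40 = 12.5% and 6/50 = 12.0%.

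**The reversal under a forms-only reading.** The documents give no contamination rates, so every rate here is assumed.

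- Six of 40 use outside care and no provider delivers a barred item. Forms alone: 0/40 = 0% (exact 95% CI 0 to 8.8%), pass. Surveys: 6/40 = 15% (5.7 to 29.8%), fail.
- Two enrollees appear on forms and four others in surveys only. Forms alone: 2/40 = 5.0%, pass. Both sources: 6/40 = 15.0%, fail. With N = 50 the figures are 2/50 = 4.0% and 6/50 = 12.0%.
- Chance of passing = P(X ≤ floor(0.10N)), X binomial with the true captured rate:

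| True captured rate | N = 40 | N = 50 |
|---|---|---|
| 5% | 95.2% | 96.2% |
| 10% | 62.9% | 61.6% |
| 15% | 26.3% | 21.9% |
| 20% | 7.6% | 4.8% |

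- If each source alone captures 6% of enrollees, independently, the union is 1 − 0.94² = 11.6%. The chance of passing falls from 91.0% to 49.5% (N = 40) or from 92.2% to 46.7% (N = 50).

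The arithmetic is sound. Whether it matters depends on whether forms alone is a reading the protocol supports.

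**What the text supports.**

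1. Aim 2b (1.2) lists prohibited treatments under acceptability and adherence, and names provider fidelity as a separate item.
2. Section 9.4.1 and Table 6 put contamination in the acceptability row and provider fidelity in a row of its own.
3. Section 9.5 groups contamination with attendance and home practice, as compliance of enrolled participants, and then turns to provider fidelity.
4. Section 5.3.3 carries the heading Prohibited Interventions, opens with the participant's restriction, and uses the same 12-week window as the target.

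A forms-only count would turn the measure into a second check on providers and leave out the outside care that Table 4 rules out. Read together, these places make outside care part of contamination, and the survey is the scheduled instrument that captures it. The forms still contribute barred items actually received from study providers.

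**Denominator.** At the 85% follow-up aimed for in 10.3.4, 34 of 40 would answer a given survey, and 4 positives would be 4/40 = 10.0% or 4/34 = 11.8%. The text settles this: 9.4.1 says enrollees and 9.5 says enrolled participants, so 4/40 applies. The 85% is also per survey. The month 1, 2 and 3 surveys all bear on the 12 weeks, so 15% missing at one of them does not mean 15% of enrollees lack all data.

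**The case for a change.** The strongest case for a change is that 5.3.3 settles the definition but not the source, and that no sentence ties either record to the target. The medication question at treatment visits in 5.1.2 is there for interaction safety. The automated queries for non-compliance in 10.3.6 serve deviation monitoring, and no field is named. A pre-specified target should not depend on an analyst's good sense, particularly when one participant can move it across the line. All of that is accurate, and the silence is real.

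The further points carry less weight.

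- **Prescriber.** That the survey omits the prescriber is inferred from a description of its domain; the items themselves are not in these documents. Rescue prescriptions come from the study's own medical provider, so they can be checked against study records.
- **Timing.** With a window of ±14 days, the month 3 survey spans about days 77 to 105 if month 3 is day 91, or days 70 to 98 if it is day 84. Either span crosses day 84, so a few reports may be hard to date. This could affect a borderline count but not the meaning of the measure.
- **Weak opioids.** The lists in 5.1.2, 5.2.2.1 and 5.3.2 are worded differently and must be reconciled on their own account. No enrollee's contamination status has been shown to turn on it.

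A rule counting any outside care for back-related leg pain, plus any item on the provider lists, would bring errors of its own. Section 5.3.2 allows specialty referral for complications and section 5 calls for referral on safety withdrawal; both would count as contamination. Section 5.2.2.3 bars recommendations, whereas the outcome is treatment received.

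**Conclusion.** No change to the plan follows. The data source and counting rule are unwritten, but the data are already collected, the denominator and by-group reporting are stated, and the placement of the measure shows that outside care is meant to count. An analyst would take both sources, count each enrollee once, leave out what the protocol permits (over-the-counter drugs, study rescue medication, protocol referrals) and report how many enrollees lack survey data.

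The largest reversal, 0% against 15% in 40 enrollees, rests on an assumed outside-care rate, an assumed absence of provider events, and a reading the text disfavours. Feasibility outcomes are analysed descriptively and qualitatively under 9.5, and section 14 gives no rule that missing this one target stops the next trial. Even at the limit the estimate is imprecise: 4/40 has an exact 95% CI of 2.8 to 23.7%, and 5/50 one of 3.3 to 21.8%. A result near 10% therefore calls for judgement whichever way it falls. The conclusion would differ if the final report counted visit forms alone, and a reader could see that from the report's methods.

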Spinal Manipulation and Patient Self-Management for Preventing Acute to Chronic Back Pain (PACBACK) study (UG3/UH3) Our team recently completed a pilot study of 92 participants with acute low back pain (UG3), which led to an ongoing randomized trial

Outcome	SMT & HE vs HE	
	12 weeks	52 weeks
Leg pain	-10% points (-19 to -2)	-7% points (-15 to 2)
Disability	-11% points (-17 to -5)	-6% points (-12 to 1)
Improvement	-11% points (-16 to -6)	-6% points (-13 to -1)
Satisfaction	-15% points (-20 to -10)	-12% points (-18 to -7)
Medication use	56% vs 63%	42% vs 66%
Less med days	OR=1.8 (1.0 to 3.1)	OR=2.6 (1.4 to 4.7)
Self-efficacy*	4% points (1 to 8)	1% point (-2 to 5)

*Not reported in primary manuscript

(n=1180, UH3). Drs. [name] and [name] (Co-Is), designed and developed a DC and PT delivered supported self-management (SSM) intervention (adapted from a Pain Coping Skills program).^{66,92,93} SSM was developed in collaboration with a multi-disciplinary group of researchers including DCs, PTs, and psychologists and consists of 4-8, 60-minute sessions, targeting the modifiable physical and psychological risk factors associated with acute LBP. Intervention elements include physical and postural exercises, integrated with cognitive strategies (e.g. relaxed breathing, progressive muscle relaxation, mental imagery), delivered with and without SMT. PTs and DCs are trained to use patient-centered communication and whole person assessment tools to tailor care to meet patient needs.

Select Pilot & Feasibility Outcomes: A total of 5 DCs and 4 PTs were trained by Drs. [name] and [name] (~20 hours). Prior to training, qualitative data suggested providers lacked the tools and training to support patients' psychosocial needs; they also expressed feeling limited in their ability to motivate patients in self-care. Provider confidence in the SSM program improved from pre-training to post-training. Patient adherence to the SSM intervention was high with 41/46 individuals (89%) attending required sessions. Follow up rates were also high (94% for weekly pain severity, 98% for monthly surveys of disability and other outcomes). These findings, along with suggestions from providers, were used to refine the SSM intervention and supporting materials for the ongoing PACBACK trial.

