5.1. Interventions, Administration and Duration

5.1.1. Supported Self-Management (SSM) - Experimental Intervention

Rationale, theory, goals: The program is theory-informed and adapted from previous cognitive behavioral and self-management programs.^{20,66,92,93} The primary goal is to enhance patients' ability to manage their BRLP symptoms in both the short and long-term by engaging in healthy physical, psychological, and social self-management behaviors (see Figure 2).^{40,51}

Description: The intervention is comprised of an integration of the following core intervention elements and 12-15 behavioral change techniques (BCTs)^{55,56} targeting important modifiable biopsychosocial factors for BRLP and which can be successfully delivered by PT or DCs. These include:

- Physical factors of strength, activity, mobility, posture, and pain symptoms;^{8,101}
- Psychological factors including beliefs (self-efficacy, fear-avoidance, catastrophizing), thoughts, emotions, and stress;^{8-10,41} and
- Social factors including social support and interpersonal relationships.

Providers will use standardized checklists for each session, to ensure they address the required elements (see 5.2.1 below).

Dose/Schedule: 6-12 sessions, up to 60 minutes per session, over 12 weeks.

Mode of delivery: One to one, in person or via videoconference when applicable; supplemented with the use of phone, videoconference, and/or email check-ins.

Location: UMN outpatient research facility or via videoconference when applicable

Tailoring and individualization: At the first session, the PT or DC will work with the patient to assess their needs and collaboratively develop an individualized treatment plan. This will include review of BPS baseline measures (see Table 5); a brief physical examination that includes manual palpation and brief postural, strength, and mobility assessments; completion of a Wellbeing Wheel (based on risk factors and the BPS model) and self-evaluation of what it would take to engage in adaptive pain behaviors (COM-B Self-Evaluation Questionnaire V1).⁵⁵ These will be re-assessed as needed. In addition, a "Self-Reliance Check In" will be completed at 6 weeks to initiate a conversation regarding release to self-care.

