5.1.2. Medical Care (MC) - Comparison Intervention

Rationale, theory, goals: The goal of medical care management for BRLP is to reduce pain and disability associated with the condition. This is achieved through the use of medications targeting pain and inflammation. Medical care is a commonly used standard approach for managing BRLP in the U.S., and thus is appropriate as an active comparison group.

Description: Medical care will be comprised of primarily medication management, which is a standard first-line approach for back-related leg pain in primary care. Choice of medications is informed by the current evidence^{12,104} and the American College of Physicians guidelines on noninvasive treatment for LBP.¹¹

- Nonsteroidal anti-inflammatory drugs (NSAIDs) will be used as a first-line approach.
- Second-line medications include systemic corticosteroids, skeletal muscle relaxants, acetaminophen, benzodiazepines, antiseizure medications, lidocaine patches, serotonin and norepinephrine reuptake inhibitors, tricyclic antidepressants and weak opioids (e.g. Tramadol, Tylenol with Codeine) for participants unable to tolerate or unresponsive to first-line medications.
- Strong opioids will not be allowed for the management of chronic BRLP, as the current CDC recommendations prefer non-opioid medications for chronic pain and there is a lack of evidence regarding their use for BRLP.^{12,105}

Medication Choice: Decisions regarding medication selection will be made collaboratively between the provider and patient after a discussion of the potential risks, benefits, past experience, and preferences for different medications.

Schedule: Minimum of 2 visits (up to 30 minutes in length) to review clinical presentation, risk/benefit profile and participant preference for first and second-line medications, and response to previous care.

Visit type: The initial visit will be in-person or via videoconference; additional visits will occur in person, by videoconference, or by phone.

Medication Delivery: Medications will be taken orally or applied topically to the skin. Injections will not be allowed. Medications will not be stored at or distributed to participants in the UMN clinic. Prescriptions for medications from the study provider will be sent to the patient's preferred pharmacy. Participants will pick up prescribed medications at their preferred pharmacy. Over the counter (OTC) medications will be picked up by the participant at their retailer of choice.

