5.4. Adherence Assessment

The total number of treatments will be decided by the treating clinician based on each individual participant's clinical presentation and response to care, as is done in clinical practice. We anticipate 6-10 visits being prescribed for most participants receiving SSM and 2-4 visits for most participants receiving medical care. Participant adherence to assigned interventions will be documented at each visit in the clinical notes.

Treatment adherence is defined as:

- Attending 2 or more Medical Care sessions or 6 or more SSM sessions
And
- Not dropping out of active treatment

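### The primary attendance target counts an SSM participant as a success at 4 sessions, while the protocol's adherence definition requires 6 or more and no drop-out, and the 4 is not explained

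*Combined protocol and SAP*

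**What the plan says.** Table 6 in section 9.4.1 lists the feasibility targets, which are the primary outcomes of the pilot. In the row on participant adherence the first target is "≥80% participants attend required sessions (SSM=4; MC=2".

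Section 5.4 defines treatment adherence by two conditions that must both hold: "Attending 2 or more Medical Care sessions or 6 or more SSM sessions", and "Not dropping out of active treatment". The same section leaves the total to the clinician ("The total number of treatments will be decided by the treating clinician") and expects 6 to 10 SSM visits for most participants.

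The SSM dose in section 5.1.1 is "6-12 sessions, up to 60 minutes per session, over 12 weeks". That section also provides for a self-reliance check-in that "will be completed at 6 weeks to initiate a conversation regarding release to self-care". Table 4 in section 5 lets provider and patient settle the number of visits together, but only after a minimum has been met; it does not state the minimum.

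For Medical Care, section 5.1.2 gives "Minimum of 2 visits (up to 30 minutes in length", which agrees with section 5.4 and with Table 6.

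The only other place where an SSM programme starts at 4 sessions is section 2.2. It describes the predecessor programme for acute low back pain, which "consists of 4-8, 60-minute sessions".

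**The concern.** One construct, adherence to the assigned treatment, has two SSM thresholds in the current text. The Table 6 row is labelled as adherence and calls its sessions required, yet its SSM count lies below both the adherence definition and the lowest dose stated for this trial. Table 6 also omits the no-drop-out condition, for both arms.

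Aim 2 assesses feasibility through pre-specified targets, and section 14 plans the phase II trial once feasibility in the Table 6 sense has been established. With Table 6 as printed, the target can be met in part by participants whom section 5.4 calls non-adherent, so attendance can look better than the protocol's own definition would show. Section 9.5 promises compliance by group, including visit attendance, but states no session threshold. Two analysts could therefore report different figures for the same primary outcome and each cite the protocol.

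**Working it through.** **1. The thresholds side by side**

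| Source | SSM | Medical Care |
|---|---|---|
| Table 6, section 9.4.1 | 4 | 2 |
| Section 5.4, adherence | 6 or more, and no drop-out | 2 or more, and no drop-out |
| Sections 5.1.1 and 5.1.2, dose | 6–12 | minimum 2 |
| Section 2.2, predecessor programme | 4–8 | not applicable |

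For Medical Care, Table 6 uses the arm's stated minimum. Had it followed the same rule for SSM, the entry would be 6. The 4 matches no dose or adherence statement for this trial. It is a definition and not the output of a formula, so there is no calculation to reproduce.

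**2. Exact shift per participant**

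Table 6 does not say whether the 80% is pooled or by arm. Pooled is the more natural reading, because the outcome is a percentage of enrollees and other Table 6 lines name the arm when they mean one. With N = 40–50 (section 9.1), one participant reclassified from success to failure moves pooled attendance by 1/N:

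- N=40: 1/40 = 2.5 points; the target needs 0.80 × 40 = 32.
- N=50: 1/50 = 2.0 points; the target needs 0.80 × 50 = 40.

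Suppose, as an assumption, that 90% meet the Table 6 rule and that k of them are SSM participants with 4 or 5 sessions:

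- N=40: (36 − k)/40. At k=3 this is 33/40 = 82.5%, still met; at k=5 it is 31/40 = 77.5%, missed.
- N=50: (45 − k)/50. At k=6 it is 39/50 = 78%, missed.

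So five SSM participants (N=40) or six (N=50) would have to stop at 4 or 5 sessions before the result changed.

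**3. Illustration from the only attendance figure in the documents**

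Section 2.2 reports that 41 of 46 (89%) attended the required sessions in the predecessor pilot. It does not say how many were required. Assume 4, that everyone attends a first session, and a constant drop-out probability h per session after that:

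- p4 = (1 − h)³ = 41/46 = 0.891, so h = 1 − 0.891^(1/3) = 0.038.
- p6 = (1 − h)⁵ = 0.825.

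The pooled count is the sum of Binomial(n, p4 or p6) for SSM and Binomial(n, m) for Medical Care, with n = 20 or 25 per arm (equal split assumed) and m = 0.90 or 0.95 (assumed). Over the four combinations, the chance of meeting the pooled target is 98% to over 99% with the cut-off at 4, and 91–98% with the cut-off at 6.

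**4. Sensitivity to the drop-out rate**

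The same model is used, with p4 = s(1 − h)³ and p6 = s(1 − h)⁵, where s is the share of SSM participants who start. All values of h are assumed; s = 0.9 uses the Table 6 allowance of 10% never treated.

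| s | h | p4 | p6 | Chance of meeting pooled target at 4 | At 6 |
|---|---|---|---|---|---|
| 1 | 3% | 91.3% | 85.9% | 99–100% | 95–99% |
| 1 | 5% | 85.7% | 77.4% | 95–99% | 81–93% |
| 1 | 7% | 80.4% | 69.6% | 88–97% | 57–75% |
| 0.9 | 3% | 82.1% | 77.3% | 91–98% | 81–93% |
| 0.9 | 5% | 77.2% | 69.6% | 80–93% | 57–75% |

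The cut-off matters little at low drop-out and noticeably at the higher rates. The figures at 6 apply the session count only; adding the no-drop-out condition could lower them further.

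**The case against.** The strongest reply is that nothing shows Table 6 to be the wrong side. A pilot may set a minimum-exposure floor for feasibility below its clinical adherence definition, and 4 could be such a floor. That stands as a possibility, and the fix allows for it. What tells against it is that the row is labelled as adherence, the stated dose starts at 6, and the Medical Care entry equals that arm's minimum. These make 6 the likelier intent, but that is inference. A reader might also infer that the 4 was carried over by mistake from the predecessor's 4–8 session programme; the documents do not link the two.

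A second reply is that a participant with 4 or 5 sessions may have been released to self-care by the clinician and need not be a drop-out. Sections 5.1.1 and 5.4 give this some support, and the model above does overstate drop-out to that extent. But Table 4 lets discretion begin only after the minimum, and the lowest SSM dose stated is 6. Section 5.4 in any case classes such a participant as non-adherent, so the conflict remains.

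A third reply is that little depends on it. Analysis is descriptive, compliance is reported by group (section 9.5), withdrawals and their reasons are reported (section 9.4.2), visits are recorded one by one (section 6.2.4), and no text makes a missed target a stop rule. All of this stands, and it limits the harm.

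A reader might infer that the lower threshold would carry the pilot over a target that it would otherwise miss. The documents do not support that. They give no session distribution or drop-out rate for this population, and the one attendance figure, read as in step 3, points to the target being met either way. The largest contrast (85–86% against 49–51% at h=5%, all starting) requires scoring the target in the SSM arm alone, which Table 6 does not say.

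**Conclusion.** The conflict is real and lies in the definition of a primary feasibility outcome: 4 SSM sessions in Table 6, against 6 or more without drop-out in section 5.4, with no explanation. Its certain size is 2.0 to 2.5 points of pooled attendance for each SSM participant with 4 or 5 sessions. Whether it would alter the pass or fail result is unknown. The probabilities rest on assumed drop-out, equal arms and assumed Medical Care attendance, and the predecessor anchor also assumes that its requirement was 4 sessions in a different, acute population. The consequence is modest. The point still deserves correction, because a pre-specified target should have one definition and choosing between 4 and 6 after seeing attendance would weaken it.

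**What to change.** Before attendance data are reviewed, set the Table 6 attendance line to the section 5.4 definition: for SSM, 6 or more sessions and not dropping out of active treatment; for Medical Care, 2 or more sessions and not dropping out. Changing only the number to 6 would leave the two definitions different. Add a supplementary row with the percentage of SSM participants reaching at least 4 sessions.

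If 4 is a deliberate feasibility floor, keep it, state that and the reason in Table 6, and report the percentage meeting the section 5.4 definition beside it.

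Section 10.3.4 has adherence measures reviewed weekly by the principal investigators and monthly by the steering committee, so the choice should be recorded early.

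The cost is one table line and one extra row. No new data are needed, since treatment is recorded at each visit and withdrawals are already to be reported. The downside is that the attendance figure may be slightly less favourable, and anyone released at 4 or 5 sessions would count against the target; the supplementary row would make that visible.
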